CLINICAL TRIAL PROTOCOL

Document Number:		c02441868-07
EudraCT No.:	2014-005395-28	
BI Trial No.:	1336.1	
BI Investigational Product(s):	BI 836880	
Title:	A First-in Human Phase I, non-randomized, open-label, multi-center dose escalation trial of BI 836880 administered by repeated intravenous infusions in patients with solid tumors.	
Brief Title:	Dose finding study of BI836880 in patients with solid tumors	
Clinical Phase:	Phase I	
Trial Clinical Monitor:	[REDACTED] Phone: [REDACTED] Fax: [REDACTED]	
Coordinating Investigator:	[REDACTED] Phone: [REDACTED] Fax: [REDACTED]	
Status:	Final Protocol (revised protocol based on global amendment 5)	
Version and Date:	Version:	Date:
	6.0	08 March 2019
Page 1 of 103		
Proprietary confidential information. © 2019 Boehringer Ingelheim International GmbH or one or more of its affiliated companies. All rights reserved. This document may not - in full or in part - be passed on, reproduced, published or otherwise used without prior written permission.		

CLINICAL TRIAL PROTOCOL SYNOPSIS

Name of company:	Boehringer Ingelheim		
Name of finished product:	not applicable		
Name of active ingredient:	BI 836880		
Protocol date: 11 May 2015	Trial number: 1336.1		Revision date: 08 March2019
Title of trial:	A First-in Human Phase I, non-randomized, open-label, multi-center dose escalation trial of BI 836880 administered by repeated intravenous infusions in patients with solid tumors.		
Coordinating Investigator			
Trial site(s):	Multi-centre trial conducted in 2 countries		
Clinical phase:	Phase I; First In Human		
Objective(s):	Objective of this trial is to determine the maximum tolerated dose (MTD) of BI 836880 and to provide preliminary safety data given as intravenous infusion and to determine recommended phase II dose. Further the PK-, immunogenicity and PD-profile, as well as primary signs of anti-tumor activity of BI 836880 should be assessed.		
Methodology:	Non-randomized, uncontrolled, open-label, dose escalating study of BI 836880 administered intravenously		
No. of patients:	About 80 patients will be entered, including at least 12 patients treated at MTD with tumour lesions evaluable for Dynamic contrast-enhanced (DCE)-MRI.		
total entered:	80		
each treatment:	80 (all patients will receive trial drug, but on different dose levels)		

Name of company:	Boehringer Ingelheim	
Name of finished product:	not applicable	
Name of active ingredient:	BI 836880	
Protocol date: 11 May 2015	Trial number: 1336.1	Revision date: 08 March2019
Diagnosis :	Advanced or metastatic/refractory solid tumors	
Main criteria for inclusion:	
 • Age \geq 18 years • Histologically or cytologically confirmed malignancy which is locally advanced or metastatic solid tumor, and either refractory after standard therapy for the disease or for which standard therapy is not reliably effective, e.g. they do not tolerate or have contraindications to otherwise available standard therapy and tumour lesions evaluable for Dynamic contrast-enhanced (DCE)-MRI at MTD • ECOG performance status \leq 2 • Adequate hepatic, renal and bone marrow functions • Signed written informed consent • Life expectancy \geq 3 months in the opinion of the investigator • Recovery from all reversible adverse events of previous anti-cancer therapies to baseline or CTCAE grade 1, except for alopecia (any grade) sensory peripheral neuropathy CTCAE grade \leq 2 or considered not clinically significant. 	
Test product(s):	BI 836880 and Diluent for BI 836880 drug product	
dose:	Starting dose will be 40 mg every 3 weeks; the dose can be increased up to 1250 mg administered every 3 weeks.	
mode of administration:	i.v.	
Comparator products:	n/a	
dose:	n/a	
mode of administration:	n/a	
Duration of treatment:	Administration of BI 836880 can be continued up to disease progression or until intolerable toxicities has been recorded.	
Endpoints	1° endpoint: 
 • assessment of the maximum tolerated dose (MTD) based on the number of patients presenting dose-limiting toxicities (DLTs) using CTCAE v4.03, started within 3 weeks after first administration of study treatment (i.e. within first 	

Name of company:	Boehringer Ingelheim	
Name of finished product:	not applicable	
Name of active ingredient:	BI 836880	
Protocol date: 11 May 2015	Trial number: 1336.1	Revision date: 08 March2019
	
cycle of treatment) and judged to be related to the study medication .
 
2° endpoints:
 
 • Exposure measures (AUC0-tz) after the first dose ; • Disposition kinetic measures (t1/2) after the first dose; • Drug related AEs leading to dose reduction or discontinuation during treatment period 	
Safety criteria:	Incidence and intensity of adverse events graded according to the common terminology criteria for adverse events (CTCAE, version 4.03), incidence of dose limiting toxicities; laboratory parameters, vital signs, ECG	
Statistical methods:	Dose escalation guided by a Bayesian logistic regression model with over dose control	

Proprietary confidential information © 2019 Boehringer Ingelheim International GmbH or one or more of its affiliated companies

FLOW CHART

Trial Periods	Screen	Treatment courses									EOT	EoR	FU / EoFU	
Course		1, 2, 3, 4					5, 6			7 ¹⁸ ongoing				
Week		w1		w2	w3	Imaging	w1	w2	Imaging	w1				
Visit	Screen	V1		V2	V3	V4	V1	V2	V3	V1				
Day; visit window [days]	-21 to -1	d1	d2	d3; +1d (1,2)*	d8; -1/+2d	d15; -1/+2d	d18; +/-3d (2,4)*	d1	d8; -1d/ +2d	d18; +/-3d (6)*	d1	EoT (when defined)	Last admin +42d; -2/+3d until PD	every 6 weeks (+/-3d)
Informed consent / IRT call	X													
Demographics	X													
Medical history	X													
Review of in-/ exclusion criteria ¹	X													
Height	X													
Weight	X	X						X			X	X		
ECOG performance status	X	X						X			X	X		
body temperature ²	X	X			X (1,2)*			X			X	X		
Blood pressure, heart rate ³	X	X (2x)**	X	X	X	X	X (2x)	X		X (2x)	X	X		
12-lead ECG ⁴	X	X (2x)**	X (1,2)*				X (2x)			X (2x)	X			
Echocardiography ⁵	X	if clinically indicated										X		
General safety laboratory parameters ⁶	X	X		X	X	X	X	X			X	X		
Serum pregnancy test ⁷	X	X					X				X	X		
Concomitant therapy	X	X	X	X	X	X	X	X			X	X	X	
Physical examination ⁸	X	X	X	X	X	X	X	X			X	X	X	
Adverse events ⁹	X	X	X	X	X	X	X	X			X	X	X	
Eligibility for treatment / IRT call ¹⁰	X						X				X			
Administration of BI 836880 ¹¹		X					X				X			
Pharmacokinetics ¹³			X	X	X	X (1,2,4)*	X (1,2,4)*		X		X (7-12)*	X	X (FU1)*	

Trial Protocol

Proprietary confidential information © 2019 Boehringer Ingelheim International GmbH or one or more of its affiliated companies

Trial Periods	Screen	Treatment courses									EOT	EoR	FU / EoFU	
Course *		1, 2, 3, 4									7 ¹⁸ ongoing			
Week		w1									w1			
Visit	Screen	V1									V1			
Day; visit window [days]	-21 to -1	d1	d2	d3; +1d (1,2)*	d8; -1/+2d	d15; -1/+2d	d18; +/-3d (2,4)	d1	d8; -1/+2d	d18; +/-3d (6)	d1	EoT (when defined)	EoT +42d; -2/+3d	every 6 weeks (+/-3d) until PD
Reason for treatment discontinuation												X		
Patients status												X	X	
Next line of anti-cancer therapy												X	X	

IRT Interactive Response Technology
ISF Investigator Site File

LMWH Low Molecular Weight Heparine
MedDRA Medical Dictionary for Drug Regulatory Activities
MTD Maximum Tolerated Dose
NC Not calculated
NCA Noncompartmental Analysis
NCI National Cancer Institute
NOA Not analysed
NOAEL No Observed Adverse Effect Level
NOP No peak detectable
NOR No valid result
NOS No sample
NSAID Nonsteroidal Anti-Inflammatory Drug
OPU Operative Unit
p.o. per os (oral)
PC Patient Completion
PD Pharmacodynamics
PD Progressive Disease
PK Pharmacokinetics

RDC Remote Data Capture
RECIST Response Evaluation Criteria In Solid Tumors
REP Residual Effect Period
SAE Serious Adverse Event
SD Stable Disease
SOP Standard Operation Procedure
SUSARs Suspected Unexpected Serious Adverse Reactions
TCM Trial Clinical Monitor
TDMAP Trial Data Management and Analysis Plan
Tie2 Receptor of the Tie Family
TME Translational Medicine Expert
TMF Trial Master File
TS Treated Set
TSAP Trial Statistical Analysis Plan

TSTAT Trial Statistician
ULN Upper Limit of Normal

1. INTRODUCTION

1.1 MEDICAL BACKGROUND

Cancer remains an important health problem with 14.1 million new cancer cases, 8.2 million cancer deaths and 32.6 million people living with cancer (within 5 years of diagnosis) in 2012 worldwide ([R14-2220](#)). Most patients with locally advanced and/or metastatic tumors are not curable and died due to their disease. There is therefore a substantial need for novel therapeutic strategies to improve the outcome of patients with advanced or metastatic malignancies who have failed conventional therapies, or for whom no therapy of proven efficacy exists. In the last decade, several novel compounds targeting specific cellular components or tumor environment, including tumor vasculature and angiogenesis have been developed based on increasing understanding of cancer biology and cell regulation.

Angiogenesis is considered as a key process in tumor growth ([R12-2552](#)). Once a certain tumor size is reached, these blood vessels are no longer sufficient and new blood vessels are required to continue growth. Acquisition of the angiogenic phenotype can result from genetic changes or local environmental changes that lead to the activation of endothelial cells. One way for a tumor to activate endothelial cells is through the secretion of pro-angiogenic growth factors (e.g. vascular endothelial growth factor, angiopoietin2, etc.) which then bind to receptors on nearby dormant endothelial cells that line the interior of vessels.

Vascular endothelial growth factor plays a major role in angiogenesis. Blockade of VEGF axis has proven to represent an efficacious treatment for patients with advanced malignancies when given in combination with cytotoxic “backbone” therapy.

Angiopoietin2 (Ang2), a ligand of the Tie2 receptor, plays an important role in angiogenesis and it's *in vivo* inhibition results in tumor growth inhibition and vasculature changes ([R12-3593](#)).

Both pro-angiogenic pathways (VEGF/VEGF-R and Ang-2/Tie-e) have been reported to synergize and to crosstalk ([R14-5320](#), [R14-5323](#)). The anticipated clinical benefit of VEGFxAng2 dual inhibition would be the modulation of tumor angiogenesis and reduced tumor growth rate.

Development of anti-angiogenic agents targeting pro-angiogenic factors is a valid concept which showed clinical efficacy in monotherapy (mainly with tyrosine kinase inhibitors: TKI) and/or in combination with standard treatment (chemotherapies) ([\(R05-2504, R09-5764, R12-5190, R14-5143, R14-5142, R14-3261, R13-5295, R14-5374, R12-0021, R14-5318\)](#)).

[figure not shown]
1.2 DRUG PROFILE

The Nanobody® technology was originally developed following the discovery that camelidae (camels and llamas) possess fully functional antibodies that lack light chains. These heavy-chain antibodies contain a single variable domain (V_{HH}) and two constant domains (CH2 and CH3). The cloned and isolated V_{HH} domain is a stable polypeptide harbouring the full

Proprietary confidential information © 2019 Boehringer Ingelheim International GmbH or one or more of its affiliated companies

antigen-binding capacity of the original heavy-chain antibody. These newly discovered V_{HH} domains form the basis of a new generation of therapeutic antibodies named Nanobodies.
[\(R15-1719\)](#)

BI 836880 is a genetic fusion protein of one VEGF-A-binding and one Ang2-binding single domain antibodies (V_{HH} , Nanobody[®]). The two single domain antibody moieties are linked via a human serum albumin-binding Alb11 domain, serving as half-life extension, and glycine-serine linkers between the domains. The protein has a molecular mass of 40.7 kDa
[\(c02353882-01\)](#)

No clinical experience has been gained in humans so far.

For a more detailed description of the drug profile refer to the current Investigator's Brochure (IB) which is included in the Investigator Site File (ISF).

2. RATIONALE, OBJECTIVES, AND BENEFIT - RISK ASSESSMENT

2.1 RATIONALE FOR PERFORMING THE TRIAL

Angiogenesis is the formation of new blood vessels from pre-existing vasculature and is a key process in tumor growth. The Ang2/Tie2 and the VEGF/VEGFR2 pathways have been identified as key pathways mediating tumor angiogenesis ([R13-0448](#)). Multiple studies have described increased VEGF levels in a variety of human cancers and the VEGF expression levels have been correlated with poor survival ([R15-1720](#)). The VEGF neutralizing monoclonal antibody bevacizumab has demonstrated anti-tumor activity in clinical trials and is currently approved for several indications and setting, mainly in combination with standard chemotherapy regimens ([R15-1222](#)).

Studies in mice have shown that Ang2, a ligand of the Tie2 receptor, controls vascular remodeling by enabling the functions of other angiogenic factors, such as VEGF ([R12-3593](#)). Ang2 is primarily expressed by endothelial cells, strongly induced by hypoxia and other angiogenic factors and has been demonstrated to regulate tumor vessel plasticity, allowing vessels to respond to VEGF and FGF2 ([R12-3834](#)).

The inhibition of Ang2 is currently being tested in Phase II/III trials of the peptibody Trebaninib in ovarian cancer. In a randomized Phase III trial in patient with recurrent ovarian cancer Trebaninib was tested in combination with paclitaxel compared to chemotherapy alone and demonstrated improvement in PFS (7.2 month vs 5.4 months, HR 0.66 95% CI 0.57-0.77, p< 0.0001) ([R14-5440](#)).

Unfortunately, the anti-tumor activity of VEGF blockers and Ang2 blockers is not durable and only a limited number of patient benefit from such therapies. New therapeutic strategies are needed to improve outcome of metastatic/advanced cancer patients.

Pre-clinical data demonstrate that improved efficacy can be achieved by combined inhibition of VEGF and Ang2 ([R14-5320](#), [R14-5323](#)). This observation was confirmed by internal data (Investigator's Brochure).

This supports testing BI 836880 in human with the objective to improve patients' outcome. First step for this clinical development is to define the safety profile of BI 836880 and the recommended dose for further development.

2.2 TRIAL OBJECTIVES

Primary objective:

- To determine the maximum tolerated dose (MTD) of BI 836880 given as intravenous infusion and to determine recommended phase II dose.

Secondary objective:

- To provide preliminary safety data

2.3 BENEFIT - RISK ASSESSMENT

BI 836880 has not been tested in human so far. In the 13 weeks toxicology study in cynomolgus monkeys BI 836880 was well tolerated up to the highest tested dose of 60 mg/kg.

Anti-VEGF or anti-VEGF-R antibodies have been largely tested in clinic with a well-defined safety profile. Most commonly reported adverse events with such compounds are fatigue, hypertension, proteinuria, diarrhea and bleeding (epistaxis). Severe adverse events include gastrointestinal perforations, tumor haemorrhage and arterial thromboembolism ([R14-3588](#), [R14-3261](#)).

There is less clinical experience with anti-Ang2 compared to VEGF pathway blockade clinical experience. The most advanced anti-angiopoietin compound (Trebaninib) in development is in Phase III in combination with chemotherapy [R14-5440](#). Other anti-Ang2 compounds are currently in early stage of clinical development ([R15-1645](#), [R15-1646](#), [R15-1648](#)). From this clinical experience the most commonly reported side effects are fatigue and gastro-intestinal symptoms (diarrhea, nausea and vomiting). No bleeding or thromboembolic events were reported with this class of compound. Of note, almost all tested anti-Ang2 molecules failed to define a MTD ([R15-1646](#), [R15-1648](#)).

Limited clinical experience of dual blockade is available. Recently, Phase I data of the bispecific human anti-Ang2/anti VEGF-A antibody (RG7221) were reported. MTD was not reached with only one dose limiting toxicity (DLT) reported (fatal pulmonary hemorrhage). Hypertension was the most common observed adverse event ([R15-1644](#)).

Based on this clinical available data it is expected that blockade of both targets will result in similar side effects as anti-VEGF and anti-Ang2 blockade. Based on the phase I trial results of RG7221 no increase in side effect severity is anticipated with BI 836880. It is anticipated that the safety profile of BI 836880 will most likely includes fatigue, hypertension, proteinuria, gastro-intestinal side effects and bleeding.

Previous clinical experience with nanobodies in different disease showed acceptable safety profile with no specific side effect related to this technology ([R13-2303](#)).

Because additional adverse event not previously observed with anti-VEGF and anti-Ang2 may also occur in humans, and taking in consideration BI 836880 toxicology study results, patients will be closely monitored for the development of adverse events that may results from BI 836880 administration, with a special attention to renal function and immunogenic side effect.

Although rare, a potential for drug-induced liver injury is under constant surveillance by sponsors and regulators. Therefore, this study requires timely detection, evaluation, and follow-up of laboratory alterations of selected liver laboratory parameters to ensure patients' safety see also [section 5.3.8.1](#).

Because of the early stage of development of BI 836880 no reproduction toxicity or genotoxicity studies were performed. Because of the advanced stage of disease of phase I studies populations, women of childbearing potential can be included into the trials. To minimize the risk of unintentional exposure of an embryo or fetus to the investigational drug, women of childbearing potential must agree to the requirements for pregnancy testing and contraceptive methods described in this protocol.

Overall, BI 836880 is expected to have an acceptable safety profile and an adequate risk/benefit in patients with locally advanced or metastatic solid tumor who are either refractory after standard therapy for the disease or for which standard therapy is not reliably effective.

3. DESCRIPTION OF DESIGN AND TRIAL POPULATION

3.1 OVERALL TRIAL DESIGN AND PLAN

This is a Phase I, non-randomized, uncontrolled, open-label, dose escalating study of BI 836880 administered intravenously. The eligible patient population will be patients with advanced solid tumors. Dose escalation will be guided by a Bayesian logistic regression model with over dose control (details refer to [Section 7](#)), restricted to a maximum of 200% dose increment for dose up to 120 mg and a maximum of 100% dose increment for dose >120 mg. At any time during the trial, it will not be permitted to escalate to a dose which does not fulfil the escalation with overdose control (EWOC) criterion (refer to Section 7).

For any dose-escalation cohort, at least 2 patients will be required. At first dose level, first patient will be treated and observed for at least 2 weeks before allowing the second patient to receive BI 836880 infusion. Subsequent enrollment at all dose levels within dose escalation, each patient in a given cohort (dose level) will be observed for a minimum of 48 hours after first BI 836880 application before allowing treatment for subsequent patient in the same cohort. In case only 2 patients are evaluable and neither has experienced a DLT within the first cycle, then dose-escalation can occur based on these 2 patients. However, should one of these 2 patients experience a DLT in the first cycle, a third patient will be enrolled on the same dose level. After all patients in a cohort have either experienced a DLT or have been observed for at least one cycle (=3 weeks) without a DLT, the Bayesian model will be updated with the newly accumulated data. The overdose risk will then be calculated for each dose, and escalation will be permitted to all doses which fulfil the EWOC criterion and dose escalation rules according to [section 4.1.3](#). Decision on further recruitment (dose escalation, de-escalation or cohort expansion will be made by a Data Safety Board (DSB) based on the collected safety data as well as other data (e.g. PK/PD data) when available.

If DLTs are observed in the first two consecutive patients of a previously untested dose level, subsequent enrolment to that cohort will be stopped. The Bayesian logistic regression model will be re-run to confirm that the dose-level still fulfils the EWOC criterion. Decision will be made whether the next patients will be enrolled on the same dose level, or if they will be enrolled to a lower dose level. [Figure 3.1: 1](#) shows how the decision of dose escalation is made.

[figure not shown]

Figure 3.1: 1: Escalation Decision – Combination of clinical and statistical expertise

BI 836880 infusion will be repeated every 3 weeks. In the case the patient shows a stable disease or even a response, the administration of BI 836880 can be continued up to disease progression or until intolerable toxicity has been recorded. In specific cases an intra-patient dose escalation can be granted (see [section 4.1.3](#)).

Once a MTD has been reached it is foreseen to enroll up to 12 patients on this dose level to enlarge the group of patients treated on proposed RP2D. A minimum of 12 patients must have tumour lesions evaluable for Dynamic contrast-enhanced (DCE)-MRI to allow a better interpretation of a pharmacodynamics (vascular) effect of BI 836880. Confirmation of the RP2D will be made based on all available safety, PK and Pharmacodynamics (PD) data at all treatment cycles and all dose levels.

In case of anti-tumor activity signals in a given tumor type, DSB can take the decision for a trial expansion to recruit patients with the same tumor type with the aim to generate safety and preliminary efficacy data specific to such disease. 2-3 tumor type expansion cohorts are planned. Up to a total of 20 patients may be recruited in each tumor type expansion cohort and will be treated according to same [Flow Chart](#) as patient in previous cohorts. This is to confirm RP2D in patient with specific tumor type according to study objective and to prepare further Phase II studies. This change will be implemented with a further amendment to this protocol.

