If infusion reaction and/or hypersensitivity reaction occurred in a substantial amount of patient (about 30%) of treated patients without premedication, premedication (as described above) prior to BI 836880 infusion will be given to all patients to be treated in the study. Such decision will be confirmed by the DSB; dosage and schedule should be aligned, but also should reflect local clinical standards.

Re-treatment criteria:

Before initiating a new treatment course the actual health status will be assessed according to [Flow Chart](#) and described in [section 5.3](#). To continue treatment with further courses, **all** of the following criteria must be met:

- No uncontrolled hypertension (according to Exclusion-Criterion #6)
- QTcF <=470 ms (according to Exclusion-Criterion #5)

- Acceptable tolerability (in case of an adverse event at the planned start of a treatment course patients may continue therapy only after recovery to a level which would allow further therapy; i.e. CTCAE grade 1 or pre-treatment value or considered not clinically significant)

In case one of the above mentioned criteria is not fulfilled the patient should be re-evaluated for up to 2 weeks. Any case of a delay in treatment course should be communicated to the Clinical Monitor at Boehringer Ingelheim. The investigator in agreement with the Clinical Monitor will decide about further treatment of individual patient, based on known risk/benefit of BI 836880.

Dose reduction guidelines

Administration of trial drug has to be stopped temporarily in case of a DLT (see [section 5.3.1](#)). Patients may continue therapy only after recovery from DLT to at least fulfil re-treatment criteria. The future dose of BI 836880 must be finally agreed on between the sponsor and the investigator. A reduction of the dose will be allowed only once for an individual patient during the whole trial. Treatment has to be discontinued in case the DLT is not reversible.

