5.3 ASSESSMENT OF SAFETY

5.3.1 Dose limiting Toxicity (DLT)

The DLT is defined as follows:

- Drug related CTCAE grade ≥ 3 non hematological toxicity with the following exceptions:
 - Vomiting or diarrhea responding to supportive treatment
 - Fatigue shorter than 4 days
 - Transient Grade 3 infusion reaction; i.e. if infusion-related reaction IRR can be controlled by appropriate medication according to Investigator's decision and next infusion will not be delayed for more than two weeks.
 - Any laboratory abnormality, which is considered not clinically relevant by the Investigator or resolves spontaneously or can be recovered with appropriate treatment (e.g.: ALK-P, GGT, Amylase, Lipase)
Clinically relevant abnormalities have to be documented as AE (see [section 5.3.8](#))
- CTCAE grade 4 neutropenia > 7 days or complicated by infection (please note, that in case of grade 4 neutropenia a more frequent follow up of patient is necessary as planned according to [Flow Chart](#)), or
- febrile neutropenia CTCAE grade ≥ 3 or
- CTCAE Grade 4 thrombocytopenia or CTCAE Grade thrombocytopenia ≥ 3 with bleeding
- Treatment delay for > 2 weeks due to unresolved drug-related adverse events, started within 3 weeks after first treatment.
- Hypertension: increase of diastolic blood pressure (BP) by 15mmHg confirmed by a second measurement or by ambulatory blood pressure measurement (when indicated; e.g. white coat effect) which can't be controlled by hypertensive medication and requests a dose reduction of BI 836880 for further treatment cycle.
- Proteinuria: urinary protein $>= 3.5$ g/day (CTCAE grade 3)

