5.3.2 Maximum Tolerated Dose (MTD)

The MTD may be considered reached if the probability that the true DLT rate is in target interval (16% - 33%) is sufficiently large. For detailed definition see statistical part ([section 7](#)). The DSB may recommend stopping the dose finding phase after the criterion for MTD is fulfilled. Further patients may be included to confirm the MTD.

If next dose level is recommended by the statistical model; however, the efficacy is considered sufficient at current dose level, the DSB may decide to include additional number of patients at this dose level, declare this dose as RP2D and no further dose escalation will happen.

Decision on next steps (dose escalation, de-escalation or cohort expansion) will be made by a Data Safety Board (DSB) based on all available safety data, including DLT information from

last cohort as described above but also findings from subsequent courses as well as other data (e.g. PK/PD data) when available.

Based on the overall data after all patients on proposed RP2D have been treated for at least 1 cycle, the DSB will make a final determination of RP2D.

Before the conclusion of the dose escalation phase and prior to the start of the expansion cohort, up to 12 patients should have been treated on the proposed RP2D.

After determination of RP2D, 2-3 expansion cohorts could be started to treat a specified patient population based on preliminary efficacy data and according to DSB decision.

All DSB decisions of dose escalation, and to open a new cohort for recruitment will be communicated to Investigators. Once MTD and RP2D is defined this information will be send to authorities.

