6.2.2 Treatment period(s)

A treatment cycle is defined as 3 weeks of duration. If initiation of a subsequent cycle is delayed due to medical reasons, additional visits beyond Day 21 may be necessary and may be performed at investigator's discretion, and should be recorded in the eCRF.

Patients may continue treatment as long as they have clinical benefit (no PD, no toxicities, no new anti-cancer treatment started) and patient is willing to continue.

During cycle 1, 2 and 4 intensive PK-sampling will be conducted and patients have to be observed closely for any adverse events. Therefore patients have to come to the clinic during the first four courses every week to the clinic. Additional visits are needed at day 2 for cycles 1, 2 and 4 and at day 3 for cycle 1. In course 5 and 6 the patient is requested to come to the clinic on day 8 after administration of study drug. From cycle 7 onwards no additional visits, beside day 1 including drug administration, are requested by protocol.

For the 2 ongoing patients, minimum set of procedures is mandatory. This includes safety lab, vital signs including blood pressure, adverse events, and pregnancy test if applicable. However, other assessments as indicated in the flowchart of the protocol or single lab values can be omitted according to investigator's opinion.

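### Protocol 3.1 allows the model update from 3 weeks, but a treatment-delay DLT can be confirmed only after more than 5 weeks, and the SAP's two-week extension is not carried into 3.1

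*Protocol*

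**What the plan says.** **Model update (protocol 3.1).** The trigger is that every patient in the cohort has had a DLT or they "have been observed for at least one cycle (=3 weeks) without a DLT, the Bayesian model will be updated with the newly accumulated data".

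**Two-patient rule (protocol 3.1).** Where only two patients are evaluable and "neither has experienced a DLT within the first cycle, then dose-escalation can occur based on these 2 patients". The protocol does not define *evaluable*. The model-update sentence does not use the word.

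**Cycle length (protocol 6.2.2).** "A treatment cycle is defined as 3 weeks of duration". A late second dose therefore does not lengthen the first cycle.

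**DLT definition (protocol 5.3.1).** The list includes "Treatment delay for > 2 weeks due to unresolved drug-related adverse events, started within 3 weeks after first treatment". A grade 3 infusion reaction escapes the list only if it can be controlled and the "next infusion will not be delayed for more than two weeks".

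**Delays (protocol 4.1.4).** "In case one of the above mentioned criteria is not fulfilled the patient should be re-evaluated for up to 2 weeks". On reporting, the section adds: "Any case of a delay in treatment course should be communicated to the Clinical Monitor at Boehringer Ingelheim".

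**DLT window (SAP 5.1 and 7.4).** The DLT evaluation period is 3 weeks, plus two more if a drug-related adverse event delays treatment. Patients evaluable for MTD are those who completed the evaluation period and were not replaced. SAP 7.4 bases the model on evaluable patients and leaves out anyone who did not finish the period for a reason other than a DLT.

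**Replacement and analysis set (protocol 3.3.4.1 and 7.3).** Patients who do not complete one 3-week cycle are replaced, unless they stopped because of a DLT. The primary analysis uses the treated set without the patients who have to be replaced.

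**The concern.** One DLT criterion resolves later than the point at which 3.1 allows the model to be updated. A patient whose second dose is on hold for a drug-related event has, at 3 weeks, been observed for one cycle without a DLT. The wording of 3.1 is then satisfied, although under 5.3.1 that patient's DLT status is still open. The SAP allows for this with its extension, but section 3.1 is the text that governs escalation. With cohorts of two or three, how one such patient is entered can decide whether the next dose meets the overdose criterion.

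The same 3- versus 5-week difference reaches the final analysis. The protocol decides replacement, and through it the primary analysis set, on 3 weeks. The SAP decides evaluability on a period that may last 5 weeks.

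**Working it through.** **1. Timing.** First dose on day 1; second dose due on day 1 + 21 = day 22; two weeks of delay reached on day 22 + 14 = day 36. A delay of more than 2 weeks therefore exists only after day 36, that is (21 + 14)/7 = 5 weeks after the first dose. The update is permitted from 3 weeks, so the gap is up to about 2 weeks. It concerns only delays caused by drug-related events, including a grade 3 infusion reaction whose exemption depends on the same delay.

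**2. Model inputs.** Protocol 7.1: logit p(d) = log α + β log(d/d\*), with the three-component mixture prior of Table 7.1:1 (weights 0.90, 0.05, 0.05). Overdose means a true DLT rate of at least 33%; the limit on its probability, P(OD), is 0.25. Posteriors were computed by grid integration.

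**3. Reproducing the plan's figures.** The protocol prints d\* = 720 mg, but its tables are recovered only with d\* = 1250 mg:

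| P(OD) | Plan | d\* = 1250 | d\* = 720 |
|---|---|---|---|
| Prior, 720 mg | 0.332 | 0.335 | 0.570 |
| Scenario 1, 120 mg | 0.044 | 0.044 | 0.063 |
| Scenario 2, 40 mg | 0.278 | 0.276 | 0.287 |
| Scenario 3, 360 mg | 0.081 | 0.078 | 0.147 |
| Scenario 4, 120 mg | 0.194 | 0.189 | 0.210 |

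Both values of d\* are carried below, so the conclusion does not depend on which was intended.

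**4. One of two patients on hold.**

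| Data | Dose considered | d\* = 1250 | d\* = 720 | Limit 0.25 |
|---|---|---|---|---|
| 0/2 at 40, 0/2 at 120 (hold entered as DLT-free) | 360 mg | 0.078 | 0.147 | met |
| 0/2 at 40, 1/2 at 120 (hold becomes a DLT) | 360 mg | 0.608 | 0.689 | failed |
| 0/2 at 40 (hold entered as DLT-free) | 120 mg | 0.044 | 0.063 | met |
| 1/2 at 40 (hold becomes a DLT) | 120 mg | 0.629 | 0.668 | failed |

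After one DLT in two, 3.1 calls for a third patient. If that patient is DLT-free (1/3), P(OD) is still 0.530 [0.620] at 360 mg and 0.508 [0.553] at 120 mg, with d\* = 720 in brackets. Both doses stay barred.

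**5. Hold with an uncertain outcome.** Let q be the chance that the hold becomes a DLT. The documents give no value, so q is an assumption shown over a range.

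P(OD) = (1 − q) × P(OD if not a DLT) + q × P(OD if a DLT).

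| q | 360 mg, d\* = 1250 | 360 mg, d\* = 720 |
|---|---|---|
| 0.1 | 0.131 | 0.201 |
| 0.3 | 0.237 | 0.309 |
| 0.5 | 0.343 | 0.418 |

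Break-even q for 360 mg:
- d\* = 1250: (0.25 − 0.0782)/(0.6083 − 0.0782) = 0.32
- d\* = 720: (0.25 − 0.1466)/(0.6893 − 0.1466) = 0.19

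For 120 mg after 40 mg the same formula gives 0.35 and 0.31.

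**6. Patient on a drug-related hold who leaves in week 4 without a DLT.**
- Protocol 3.3.4.1: the 3-week cycle is complete, so the patient is not replaced.
- Protocol 7.3: not replaced, so **included** in the primary analysis.
- SAP 5.1 and 7.4: the extended period was not completed, and not because of a DLT, so **excluded**.

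If this happens at 120 mg after 0/2 at 40 mg, P(OD) at 360 mg is 0.078 [0.147] with the patient included (0/2) and 0.099 [0.174] with the patient excluded (0/1). Both meet the limit, so here the two documents disagree about who is analysed, not about whether the limit is met.

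**The case against.** Several safeguards count against a strong reading.

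- *At least one cycle is a minimum.* This stands: 3.1 does not force an update at 3 weeks.
- *The two-patient rule speaks of evaluable patients.* If the SAP meaning applies, a patient on hold does not count towards the two. This stands for that sentence, although the protocol neither defines the term nor refers to the SAP for it. The model-update sentence has no such qualifier.
- *Section 3.1 bars escalation at any time to a dose that fails the overdose criterion.* A hold that becomes a DLT before the next cohort starts must therefore be respected. This narrows the gap but does not say how a hold still open at the update enters the model.
- *The DSB should know of the hold.* Delays are reported to the sponsor's monitor, and under 5.3.2 the DSB uses safety data from the last cohort "but also findings from subsequent courses as well as other data (e.g. PK/PD data) when available". Knowing of the hold is not a rule for coding it.
- *Section 3.1.1 leaves the minimum data for escalation to the DSB charter.* The charter is not among the documents and may settle the point.
- *Escalation may be over.* Version 6.0 refers to two ongoing patients. If so, rewording 3.1 changes no dose decision, but the analysis-set conflict remains.

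A reader might infer that the trial did escalate on patients with open holds. Nothing in the documents shows this. A reader might also take Table 10.6:1 as displaying the effect. It compares 0/2 with 1/3 and has no patient on hold. Nor should the reversal be extended to higher dose levels, where it depends on which reference dose is used.

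**Conclusion.** The mismatch is real and worth correcting. Protocol 3.1 permits, but does not require, a model update that enters a patient on hold as DLT-free up to about two weeks before the delay criterion can be judged. The SAP's extension is not carried into 3.1. The safeguards narrow the gap; the documents do not show that it is closed.

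If the hold becomes a DLT, the decision reverses at each of the first two dose levels under either reference dose. If the outcome is uncertain, the limit at 360 mg is passed only once the assumed chance of a DLT exceeds about 0.32 (d\* = 1250) or 0.19 (d\* = 720); a hold unlikely to become a DLT would not change that decision.

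The analysis-set conflict is narrow, since it needs a patient who leaves on a drug-related hold between weeks 3 and 5, but it does not depend on the DSB charter or on whether escalation continues. It assumes that the SAP's DLT evaluation period and MTD evaluation period, which it never expressly equates, are the same period.

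**What to change.** Reconcile protocol 3.1, 3.3.4.1, 5.3.1, 6.2.2 and 7.3 with SAP 5.1 and 7.4, so that:

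- the model update, replacement and the final MTD set use one DLT evaluation period under one name;
- a patient still inside that period is not entered in the model as a non-DLT;
- the week-4 leaver is treated the same way for replacement and for analysis.

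If the DSB charter already covers patients on hold, cite it in 3.1. If escalation is complete, the change applies to the final MTD set.

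Cost: wording edits in both documents and, during escalation, up to about two weeks' wait for a cohort with a patient on hold.
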